4.2 Site Registration

This study is supported by the NCI Cancer Trials Support Unit (CTSU).

Each investigator or group of investigators at a clinical site must obtain IRB approval for this protocol and submit IRB approval and supporting documentation to the CTSU Regulatory Office before they can be approved to enroll patients. Assignment of site registration status in the CTSU Regulatory Support System (RSS) uses extensive data to make a determination of whether a site has fulfilled all regulatory criteria including but not limited to the following:

- An active Federal Wide Assurance (FWA) number
- An active roster affiliation with the Lead Network or a participating organization
- A valid IRB approval
- Compliance with all protocol specific requirements.

In addition, the site-protocol Principal Investigator (PI) must meet the following criteria:

- Active registration status
- The IRB number of the site IRB of record listed on their Form FDA 1572
- An active status on a participating roster at the registering site

Sites participating on the NCI CIRB initiative that are approved by the CIRB for the study are not required to submit separate IRB approval documentation to the CTSU Regulatory Office. For sites using the CIRB, IRB approval information is received from the CIRB and applied to the RSS in an automated process. Signatory institutions must submit a Study Specific Worksheet for Local Context (SSW) to the CIRB via IRBManager to indicate their intention to open the study locally. The CIRB's approval of the SSW is then communicated to the CTSU Regulatory Office. In order for the SSW approval to be processed, the Signatory Institution must inform the CTSU which CIRB-approved institutions aligned with the Signatory Institution are participating in the study.

4.2.1 Downloading Regulatory Documents

Site registration forms may be downloaded from the 10089 protocol page located on the CTSU Web site. Permission to view and download this protocol is restricted and is based on person and site roster data housed in the CTSU RSS. To participate, Investigators and Associates must be associated with the Corresponding or Participating protocol organization in the RSS.

- Go to https://www.ctsu.org and log in using your CTEP-IAM username and password.
- Click on the Protocols tab in the upper left of your screen.
- Either enter the protocol # in the search field at the top of the protocol tree, or

- Click on the By Lead Organization folder to expand, then select LAO-MN026, and protocol # 10089.
- Click on LPO Documents, select the Site Registration documents link, and download and complete the forms provided. (Note: For sites under the CIRB initiative, IRB data will load to RSS as described above.)
- 4.2.2 Requirements For Protocol 10089 Site Registration:
 - IRB approval (For sites not participating via the NCI CIRB; local IRB documentation, an IRB-signed CTSU IRB Certification Form, Protocol of Human Subjects Assurance Identification/IRB Certification/Declaration of Exemption Form, or combination is accepted)
 - Site Initiation Visit
- 4.2.3 Submitting Regulatory Documents

Submit required forms and documents to the CTSU Regulatory Office, where they will be entered and tracked in the CTSU RSS.

Regulatory Submission Portal: www.ctsu.org (members' area) \rightarrow Regulatory Tab \rightarrow Regulatory Submission

When applicable, original documents should be mailed to:

CTSU Regulatory Office [name]

Institutions with patients waiting that are unable to use the Portal should alert the CTSU Regulatory Office immediately at [name] in order to receive further instruction and support.

4.2.4 Checking Site Registration Status

You can verify your site registration status on the members' section of the CTSU website.

Go to https://www.ctsu.org and log into the members area using your CTEP-IAM username and password.

Click on the Regulatory tab at the top of your screen.

Click on the Site Registration subtab.

Enter your 5-character CTEP Institution Code and click on Go.

Note: The status given only reflects compliance with IRB documentation and institutional compliance with protocol-specific requirements as outlined by the Lead Network. It does not reflect compliance with protocol requirements for individuals participating on the

protocol or the enrolling investigator's status with the NCI or their affiliated networks.

4.3 **Patient Registration**

4.3.1 OPEN / IWRS

Patient enrollment will be facilitated using the Oncology Patient Enrollment Network (OPEN). OPEN is a web-based registration system available to users on a 24/7 basis. It is integrated with the CTSU Enterprise System for regulatory and roster data interchange and with the Theradex Interactive Web Response System (IWRS) for retrieval of patient registration/randomization assignment. Patient enrollment data entered by Registrars in OPEN / IWRS will automatically transfer to the NCI's clinical data management system, Medidata Rave.

The OPEN system will provide the site with a printable confirmation of registration and treatment information. Please print this confirmation for your records.

4.3.2 OPEN/IWRS User Requirements

OPEN/IWRS users must meet the following requirements:

- Have a valid CTEP-IAM account (*i.e.*, CTEP username and password).
- To enroll patients: Be on an ETCTN Corresponding or Participating Organization roster with the role of Registrar.
- To access cohort management: Be identified to Theradex as the "Client Admin" for the study.
- Have regulatory approval for the conduct of the study at their site.

Prior to accessing OPEN/IWRS, site staff should verify the following:

- All eligibility criteria have been met within the protocol stated timeframes.
- If applicable, all patients have signed an appropriate consent form and HIPAA authorization form.

4.4 General Guidelines

Following registration, patients should begin protocol treatment within 7 days. Issues that would cause treatment delays should be discussed with the Principal Investigator. If a patient does not receive protocol therapy following registration, the patient's registration on the study may be canceled. The Study Coordinator should be notified of cancellations as soon as possible.

5. TREATMENT PLAN

5.1 Agent Administration

Treatment will be administered on an outpatient basis. The study drugs may be administered in sequence, without regard to order. Do not administer study drugs concurrently. For patients receiving both drugs, the intravenous catheter must be flushed with 0.9% sodium chloride between the two infusions. Pre-medication is not needed unless a patient develops an infusion reaction.

Patients will be randomly allocated for treatment in one of two groups (group 1 or group 2). Both groups will receive Nivolumab at the dose of 240 mg IV every 2 weeks for the first 4 months on the study. After four months, Nivolumab will be administered at the dose of 480 mg IV every 4 weeks. Patients allocated to group 2 will also receive CDX-1127 (varilumab) at the dose of 3 mg/kg IV every 4 weeks. Response assessment will be performed every 12 weeks. Patients in group 1 (nivolumab alone) who meet criteria for disease progression at any point in the study will be allowed to cross-over to group 2 (nivolumab and CDX-1127 (varilumab) and continue on the study. A repeat biopsy is mandatory for patients who wish to cross-over from group 1 to group 2 at the time of disease progression.

Reported adverse events and potential risks are described in Section 7. Appropriate dose modifications are described in Section 6. No investigational or commercial agents or therapies other than those described below may be administered with the intent to treat the patient's malignancy.

5.1.1 CDX-1127 (Varlilumab)

CDX-1127 (Varlilumab) will be given every four weeks ± 2 days at a dose of 3 mg/kg. Patients may be dosed no less than 26 days from the previous dose of drug.

CDX-1127 (Varlilumab) is to be administered as a 90-minute intravenous (IV) infusion

using a 0.2 - 0.22 micron in-line filter connected to the infusion set. CDX-1127 (Varlilumab) should not be administered as a bolus injection. All patients should be monitored for 4-6 hours following the first two doses and 2 hours following all subsequent doses; patients who experience any treatment-related adverse events during the observation period should be further monitored as clinically appropriate (*e.g.*, for up to 24 hours post-dose).

CDX-1127 (Varlilumab) cannot be mixed with any other drug in the infusion bag or the administration set.

5.1.2 Nivolumab

Nivolumab will be given every two weeks ± 2 days at a dose of 240 mg for 4 months followed by 480 mg every 4 weeks thereafter. Patients may be dosed no less than 12 days from the previous dose of drug during cycles 1 - 5 and no less than 26 days from the previous dose beginning with cycle 6.

There will be no dose modifications allowed.

Nivolumab is to be administered as a 30-minute IV infusion, using a volumetric pump with a 0.2-1.2 micron in-line filter at the protocol-specified dose. The drug can be diluted with 0.9% normal saline for delivery but the total volume must not exceed 160 mL. It is not to be administered as an IV push or bolus injection. At the end of the infusion, flush the line with a sufficient quantity of normal saline.

5.2 General Concomitant Medication and Supportive Care Guidelines

Because there is a potential for interaction of CDX-1127 (varlilumab) and nivolumab with other concomitantly administered drugs, the case report form must capture the concurrent use of all other drugs, over-the-counter medications, or alternative therapies. Appendix B, the Patient Wallet Card, will be given to patients to identify the study physician and provide a contact telephone number.

5.3 **Duration of Therapy**

In the absence of treatment delays due to adverse event(s), treatment may continue for up to a maximum of 2 years or until one of the following criteria applies:

- Disease progression (except patients on group 1 who wish to cross-over to group 2),
- Intercurrent illness that prevents further administration of treatment,
- Adverse event(s) which require(s) permanently going off study treatment (see also section 6 and specific algorithms in Appendix E)
- Any dosing interruption lasting > 6 weeks, with the following exceptions: Dosing

interruptions > 6 weeks that occur for non-drug-related reasons may be allowed if approved by the Investigator. Prior to re-initiating treatment in a subject with a dosing interruption lasting > 6 weeks, the Principal Investigator must be consulted.

- Patient decides to withdraw from the study
- General or specific changes in the patient's condition render the patient unacceptable for further treatment in the judgment of the investigator
- Clinical deterioration as defined by acute or progressive decline in performance status, progressive debility or progressive increase in tumor-associated symptoms that negatively impact the patient's quality of life as judged by the treating physician.
- Patient non-compliance
- Pregnancy
 - All women of child bearing potential should be instructed to contact the investigator immediately if they suspect they might be pregnant (e.g., missed or late menstrual period) at any time during study participation.
 - The investigator must immediately notify CTEP in the event of a confirmed pregnancy in a patient participating in the study.
- Termination of the study by sponsor
- The drug manufacturer can no longer provide the study agent

The reason(s) for protocol therapy discontinuation must be documented in the Case Report Form (CRF).

5.4 Duration of Follow Up Following End of Therapy

Patients will be followed for additional 100 days (based on 5 half-lives) after end of therapy or until death, whichever occurs first. Patients removed from therapy for unacceptable adverse event(s) will be followed until resolution or stabilization of the adverse event.

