5.5 Criteria for Removal from Study

Patients treated in group 1 (Nivolumab alone) are allowed to cross-over to group 2 at the time of documented disease progression. A repeat biopsy is mandatory to confirm progressive disease. Patients who cross-over from group 1 to group 2 may continue treatment for an additional 2 years (counting from the start of treatment on group 2) as long as he or she does not meet other criteria for removal from the study.

Patients will be removed from study when any of the applicable criteria occur: completion of follow-up as described in Section 5.4 above, patient withdrawal, or

inability to follow study protocol as listed in Section 5.3. The reason for study removal and the date the patient was removed must be documented in the Case Report Form.

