c.	A pre-study biopsy is mandatory for all groups and must be obtained within 60 days prior to registration. For Group 1 patients who elect to cross over to Group 2, a biopsy is mandatory at that time. An off-study biopsy is optional for all groups.
d:	Off-study evaluation to be performed 30 days (+/- 14 days) after the last dose of study drug. Patients are followed for at least 100 days for AE assessment.
e:	As clinically indicated, perform an evaluation of cardiac function including ECG and echocardiogram for any patients with a history of CHF or at risk because of underlying cardiovascular disease or exposure to cardiotoxic drugs. Also perform an evaluation for patients with evidence of CHF, MI, cardiomyopathy, or myositis including lab tests and cardiology consultations including ECG, echocardiogram, CPK and troponin.
f:	Blood draw for correlative studies will be obtained at baseline (within 14 days prior to start of protocol therapy) and within 72 hours prior to the administration of any of the study drugs on dosing days. These blood draws may be performed at the same occasion as other laboratory tests obtained for the purpose of clinical monitoring of the patient. Patients who cross-over from Group 1 to Group 2 will need 4 additional blood draws pre-dose prior to their first 4 infusions of CDX-1127 (varlilumab) for immunogenicity and PK studies.
g:	A serum or urine pregnancy test is required within 24 hours of starting study treatment. If the pre-study assessment was performed within 24 hours prior to start of study treatment, a pregnancy test does not need to be repeated.
*:	Starting with Cycle 5 (Week 17), the dosage and administration schedule of nivolumab is changed to 480 mg every 4 weeks. The dosage and administration schedule of CDX-1127 (varlilumab) remains unchanged. Once the schedule of administration of nivolumab changes, the frequency of routine evaluations also changes accordingly to every 4 weeks as

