11.1.3 Schedule of Evaluations

PET/CT scans are required at baseline for all patients. Repeat PET-CT scans should be obtained every 12 weeks unless otherwise clinically indicated.

Definitions for clinical response for patients with lymphoma are based on the lymphoma response to immunomodulatory therapy criteria or LYRIC (Cheson *et al.*, 2016). Lymph node measurements should be taken from the CT portion of the PET/CT, or other dedicated CT scans where applicable. Measurement of lymphadenopathy for purposes of assessing for PR will be determined by adding the sum of the products of the maximal perpendicular diameters of measured lesions (SPD). The perpendicular diameter of a single node is sufficient to evaluate for PD (see Table 11.1.4). Measurable extranodal disease should be assessed in a manner similar to that for nodal disease. For these recommendations, the spleen is considered nodal disease. Disease that is only assessable (*e.g.*, pleural effusions, bone lesions) will be recorded as present or absent only, unless, while an abnormality is still noted by imaging studies or physical examination, it is found to be histologically and pathologically negative.

For response assessment, PET-CT is preferred for staging of FDG-avid lymphomas and CT scan is preferred in the other lymphomas

Progressive disease is based on either PET-CT based (PMD) or CT based (PD) response criteria. Definition of progressive disease according to LYRIC is same as the Lugano classification except that a new category of indeterminate response (IR) is added. Patients whose disease fall in the IR category may continue treatment for additional 12 weeks if the patient remains clinically stable as judged by the treating physician. A repeat imaging

study in 12 weeks (or earlier if clinically indicated) is mandatory to confirm or refute disease progression. PET confirmation of progressive disease is per physician discretion.

11.1.4 Lymphoma Response to Immunomodulatory Therapy Criteria [LYRIC] (adapted from Cheson *et al.*, 2016)

	PET-CT Based Response	CT-Based Response
Complete Response (CR)	Complete metabolic response (CMR)	Complete radiologic response (CR) (all of the following)

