Final Decision Rule: The final analysis will take place after all 48 evaluable patients in each group have been followed for at least 6 months. The response rates will be compared between the two groups using Fisher's exact test. If the response rate is higher in Group 2 the experimental group, where the p-value < 0.15, this will be considered sufficient evidence that Group 2 the experimental group may be recommended for further testing in subsequent studies. Otherwise, we will conclude that there is not statistical evidence of superiority of the experimental regimen.

Over Accrual: If more than the target number of patients are accrued, the additional patients will not be used to evaluate the stopping rule or used in any decision making process however, they will be included in final point estimates and confidence intervals.

NOTE: The trial will not be halted while the first 24 patients in each group are evaluated for the interim analysis. However, if the accrual is especially rapid, we may temporarily suspend accrual to prevent missing important acute toxicity patterns.

Other Considerations: Toxicity, quality/duration of response, and patterns of treatment failure observed in this study, as well as scientific discoveries or changes in standard care will be taken into account in any decision to terminate the study.

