13.1.4 Analysis Plan

The analysis for this trial will commence at planned time points and at the time the patients have become evaluable for the primary endpoint. Such a decision will be made by the Statistician and Study Chair, in accord with ETCTN Standard Operating Procedures, availability of data for secondary endpoints (eg, laboratory correlates), and the level of data maturity. It is anticipated that the earliest date in which the results will be made available via manuscript, abstract, or presentation format is when the last patient has been followed for at least 6 months.

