13.2.2 Accrual Rate and Study Duration

The anticipated accrual rate is approximately 5-6 patients per month. Therefore, the accrual period for this phase 2 study is expected to be about 20 months. The final analysis can begin approximately 26 months after the trial begins, i.e. as soon as the final patient accrued to this trial has been followed for at least 6 months.

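### Follow-up stops 100 days after therapy and no survival contact is planned, so overall survival is censored according to prognosis, deaths go unrecorded, and the direction of the resulting bias cannot be known

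*Combined protocol and SAP*

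**What the plan says.** OS is a secondary objective (section 1.2). Section 13.4.2 measures it from randomisation to death from any cause, with Kaplan-Meier curves and a log-rank test between arms. It gives no censoring rule. Section 13.4.1 has one for duration of response; section 13.4.3, on progression-free survival, has none.

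Follow-up after treatment is set in section 5.4: "Patients will be followed for additional 100 days (based on 5 half-lives) after end of therapy or until death, whichever occurs first". The only extension is for patients taken off therapy for an unacceptable adverse event, who are followed until it resolves or stabilises. Section 5.5 adds: "Patients will be removed from study when any of the applicable criteria occur: completion of follow-up as described in Section 5.4 above". Footnote d of the study calendar (section 10) says "Patients are followed for at least 100 days for AE assessment", which is a safety purpose. The calendar has no survival row.

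Section 5.3 lists what ends therapy. One entry reads "Disease progression (except patients on group 1 who wish to cross-over to group 2"; others are clinical deterioration, adverse events, intercurrent illness and withdrawal. Crossover patients may be treated for up to 2 further years (section 5.5). Scans are 12-weekly, and a patient with an indeterminate response "may continue treatment for additional 12 weeks if the patient remains clinically stable" (section 11.1.3).

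On timing, section 13.1.3 says "The final analysis will take place after all 48 evaluable patients in each group have been followed for at least 6 months". Section 13.1.4 expects results no sooner than "when the last patient has been followed for at least 6 months", and section 13.2.2 starts the final analysis "as soon as the final patient accrued to this trial has been followed for at least 6 months", about 26 months after the trial opens.

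**The concern.** Kaplan-Meier and log-rank methods assume that patients censored at a given time have the same later death risk as those still observed. Here the 100-day clock starts when therapy ends, and therapy often ends because the disease has worsened. Patients who do well stay under observation for up to 2 years plus 100 days. Patients who do badly leave about 100 days after stopping, and later deaths have no planned route into the database.

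Two things are at stake. Deaths before the cut-off are lost, which costs information even when there is no bias. The OS curves are also exposed to dependent censoring. The exposure differs by arm, because a Group 1 patient who crosses over stays on study past first progression and a Group 2 patient does not.

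**Working it through.** **The plan's own figures.** The documents give no OS hazard, event target or power, so there is no OS figure to reproduce. The stated size, 48 per group for response rates of 25% against 45% at one-sided 0.15, does reproduce: exact power of the one-sided Fisher test is 80.9%. That calculation does not involve OS.

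**Inputs from the documents.** 100 days of follow-up after therapy (5.4); therapy to progression or 24 months (5.3); scans every 84 days (5.1, 11.1.3); accrual over 20 months and cut-off at month 26 (13.2.2).

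**Assumed inputs.** Median time to progression 2-4 months and median post-progression survival 3-9 months, in seven pairs (2/3, 2/9, 2.5/4, 3/6, 4/3, 4/6, 4/9). Pre-progression death hazard is r times the post-progression hazard, with r = 0, 0.25 or 0.5. All times are exponential.

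**Model.** Observed time = min(death, end of therapy + 100 days, cut-off). Bias = Kaplan-Meier at 12 months minus true 12-month survival. Each pair was simulated with 400,000 patients, without crossover (Group 2).

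| When progression is found | Quantity | r = 0 | r = 0.25 | r = 0.5 |
|---|---|---|---|---|
| At 12-weekly scans | Bias, points | 4.0 to 7.1 | 2.5 to 4.6 | 1.2 to 2.7 |
| | Deaths not recorded | 26-49% | 19-46% | 15-42% |
| Scans, 25-50% of patients extended 12 weeks | Bias, points | 1.8 to 5.4 | 1.0 to 3.7 | 0.5 to 2.1 |
| | Deaths not recorded | 18-45% | 13-41% | 11-38% |
| At once | Bias, points | 8.1 to 12.4 | 4.5 to 8.1 | 2.3 to 4.6 |
| | Deaths not recorded | 39-64% | 29-58% | 23-54% |

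For the 3/6 pair at scan timing, true 12-month OS of 43.8%, 37.3% and 32.4% reads 50.2%, 41.6% and 34.9%. With equal hazards (r = 1) the bias is zero, yet 25% of deaths in that pair are still lost. With follow-up to the cut-off, Kaplan-Meier is within 0.1 point of the truth.

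**Does the direction survive other assumptions?** Three changes were tried, all scan-timed.

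- Mixed prognosis: the post-progression hazard is halved in half the patients and doubled in the rest. The bias becomes -0.1 to +4.6 (r = 0), -1.4 to +2.8 (r = 0.25) and -2.4 to +1.3 (r = 0.5). If the pre-progression hazard is scaled in the same way, the range over all three r is about -0.4 to +4.6.
- Falling hazard (per month): 0.02 before progression, 0.20 for 100 days after it, then 0.06. True OS of 42.1% reads 37.3%, which is -4.8. With 0.10 as the late value, 37.5% reads 37.4%.
- Lower hazard after progression (0.10 before, 0.05 after): -3.7.

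The bias can reverse because high-risk patients may die inside the 100-day window and be counted. Those then censored are survivors with a lower risk than the patients still observed.

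**Between arms.** With equal true survival, constant post-progression hazards and scan timing, the Group 2 to Group 1 hazard ratio is about 1.00 without crossover and 0.89-0.99 with 50-80% random crossover. It is 0.98-1.03 when fitter patients are the ones who cross over. If progression is found at once, the last two ranges widen to 0.793-0.980 and 0.928-1.053.

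**The 6-month wording.** Six months is 182.6 days, and 182.6 - 100 = 82.6. A patient whose therapy ends before about day 83 can therefore leave the study before 6 months. One stopped at the first scheduled scan reaches day 84 + 100 = 184.

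**The case against.** The strongest objection is to direction. A reader might infer that, if death risk is higher after progression than before it, the OS curves must read too high. The documents give no hazards, and the inference fails without a roughly constant post-progression hazard. In the mixed-prognosis case at r = 0.25 every patient's risk rises at progression, yet the 2/3 pair reads 1.4 points too low. This objection stands.

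A reader might also infer that the 100-day rule contradicts a 6-month minimum. The three sentences mainly time the analysis: 20 months of accrual plus 6 gives 26. Read as a retention rule, they could not be met by anyone who died before 6 months. What remains is a need for clarification.

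A third tempting reading is that longer follow-up of crossover patients tilts the log-rank test towards the combination. That appears under random crossover but not consistently when crossover depends on prognosis, and the documents give no crossover rate.

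The model is also simple: it stops therapy only at progression or 24 months, whereas section 5.3 lists many reasons. The consequence is limited too. The binomial standard error of 12-month OS near 40% with 48 patients is sqrt(0.4 x 0.6 / 48) = 7.1 points, so the largest scan-timed bias is about one standard error. OS is secondary and unpowered, and permitted crossover already limits it as a comparison with nivolumab alone.

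None of this supplies the missing survival follow-up or the missing censoring rule.

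**Conclusion.** The gap is real: as written, follow-up ends 100 days after therapy, no visible section plans survival contact, and OS is still tested between arms without a censoring rule. Censoring will depend on prognosis and will differ by arm through crossover.

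In the scan-timed, constant-hazard illustrations with r from 0 to 0.5, about 15-49% of deaths before cut-off go unrecorded and 12-month OS reads about 1-7 points high. These figures rest on assumed rates. The bias falls to near zero or changes sign under other plausible hazard shapes, so neither its direction nor its size can be settled from the plan. That uncertainty is itself the reason to collect the deaths. The primary endpoint and the go/no-go rule are untouched. This is an inexpensive change that should be made, and it is not a threat to the trial's main conclusion.

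**What to change.** - In sections 5.4 and 5.5, separate the 100-day safety follow-up from survival follow-up. Collect vital status by phone, chart or public record about every 3 months on every randomised patient to the final-analysis cut-off, whatever their therapy or crossover status, subject to consent. Add this to the calendar in section 10.
- In section 13.4.2, state that OS is censored at the last date known alive.
- In sections 13.1.3, 13.1.4 and 13.2.2, clarify how the 6-month wording fits the 100-day rule.
- If survival follow-up is not added, drop the OS log-rank test and report OS descriptively, with a caveat on dependent censoring. This is a wording change only.

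The main fix costs a protocol amendment, a check that consent covers the contact (the consent pages are not available here), and contacts for up to 106 patients. Mean potential follow-up is (26 + 6) / 2 = 16 months, so about 16 / 3, or 5, contacts per patient on average, and fewer for those who have died or are still on therapy. It adds no visits, scans or procedures. It does not remove the limit that crossover places on the OS comparison.
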